10 DATA HANDLING AND RECORDS RETENTION

Study records and reports, including, but not limited to, electronic case report forms (eCRFs), source documents, informed consent forms, laboratory test results, and medication inventory records, shall be retained for at least 2 years after study completion, but potentially longer based on local institutional requirements.

10.1 Data collection and management

The amount of data that will be collected for the proposed feasibility study will be limited in quantity, but a large, multisite study based on this feasibility study would be substantial and would require a sophisticated, practical and flexible system that can accommodate different modes of data collection and several separate linked surveys. The novel Vanderbilt-designed resource developed specifically for online collection of research information, the REDCap platform, will be used to design study forms, including the reaction forms, and short customized questionnaires to collect information from study subjects. This system will be used by Vanderbilt, Cincinnati and Duke for data management. All electronic linkages will fulfill regulations for protection of human subjects and requirements to minimize the risk of breach of confidentiality. After initial set-up, the work load required for electronic data collection will be substantially reduced (description of REDCap resources below).²² The Vanderbilt, Cincinnati and Duke investigators have previously used the REDCAP system for collection and analysis of large quantities of data. Participants' parents/guardians will be given the option to fill out their reactogenicity diary either directly in the REDCap system or on paper. Participants who choose the paper form will receive a phone call on day 3-6, 7-9, 14-17, 27-31, and 44-47 post-vaccination to collect the information recorded on their memory aid, which will then be entered by study personnel onto REDCap. All study-related documents containing protected health information, e.g. enrollment logs, case report forms, memory aids completed by study participants, will be maintained in secure research offices at Vanderbilt, Cincinnati and Duke, respectively, which are accessible to research staff only.

Vanderbilt Research Electronic Data Capture (REDCap)

Investigators within the NIH-funded Clinical and Translational Research Unit at Vanderbilt have developed REDCap, to collect and manage data for diverse clinical and translational research studies.²² REDCap was designed around the concept of giving research teams an easy method to specify project needs and rapidly develop secure, web-based applications for collection, management and sharing of research data. REDCap accomplishes these key functions through use of a single study metadata table referenced by presentation-level operational modules. Based on this abstracted programming model, databases are developed in an efficient manner with little resource investment beyond the creation of a single data dictionary. The concept of metadata-driven application development is well established, and the critical factor for successful data collection lies in creating a simple workflow methodology allowing research teams to autonomously develop study-related metadata in an efficient manner. Of particular interest for this project, a subcomponent of REDCap, the REDCap Survey is designed for studies where data are collected directly from the research participant. This will be used with the web-based reaction forms that will be completed by the study subjects' parents/guardians. Both products include secure institutional data hosting and include full audit-trails in compliance with HIPAA security requirements. The REDCap Consortium is comprised of 647 active institutions, including CCHMC and Duke Health Technology Solutions. The REDCap currently supports 68,000 projects with over 89,000 users spanning numerous research focus areas across the consortium. The current project will use this software application for the design of electronic forms to collect information

from study participants, to link the baseline data, sample collection date, and laboratory results in an automated database family, to perform data cleaning and data quality assurance efficiently, and to design an analytical dataset for the analysis of the project data.

Double data entry

Double data entry for each record is a means of ensuring quality data collection by later comparing the records. We will create two identical REDCap databases to store our data, each site can designate two data entry persons to enter each database. Or if there is only one data entry person, then at least 7 days lagging time between entering same participants' info into these two databases will be required to reduce/remove memory residual, in other words, same participants' info can't be entered into both databases within 7 days. For example, participants 1-10 and 11-20 can be entered into database 1 and 2 this week respectively, and next week they can be switched and entered into the other database respectively. From previous experience, seven days waiting period is long enough to minimize memory residual effect.

Both the leading site and the collaborating sites will use REDCap to collect subjects' information and all sites will do double data entry. CDC can use REDCap as a means of monitoring the study. Data will be entered into REDCap in a timely manner by experienced data entry personnel. Periodic data enrollment audits will be conducted through the recruitment period to ensure that we are not missing appropriate children and help monitor study progress. Comparisons of double data entry will be conducted and a list of discrepancies between two databases will be generated for each site on a regular basis.

Data cleaning and data quality assurance

In order to perform data cleaning and data quality assurance efficiently, double data entry will be performed with numerous built-in filters and checks for consistency of the data including range and limit checks, branching logic and pull down menus to limit choices for categorical variables to a pre-specified list will be implemented and performed automatically to minimize data entry error. The data will be randomly sampled and checked against source records on a regular basis. The data and related analytical datasets will also be stored in the Department of Biostatistics with secured password-protected computers at Vanderbilt University. Data cleaning check and error reports will be generated on a regular basis for all sites.

Role of the CDC Investigators in the Project

11 ETHICS/PROTECTION OF HUMAN SUBJECTS

11.1 Ethical Standard

The site principal investigators will ensure that this trial is conducted in full conformity with principles of the *Belmont Report: Ethical Principles and Guidelines for the Protection of Human Subjects of Research of the National Commission for the Protection of Human Subjects of Biomedical and Behavioral Research (April 18, 1979)* and codified in 45 CFR 46 and ICH E6; 62 Federal Regulations 25691 (1997), if applicable. The site principal investigator's Institution will hold a current Federal Wide Assurance (FWA) issued by the Office of Human Research Protection (OHRP) for federally funded research.

11.2 Institutional Review Board

Prior to enrollment of subjects into this trial, the approved protocol and informed consent form will be reviewed and approved by the appropriate IRB.

11.3 Informed Consent Process

Informed Consent

The site principal investigator will choose subjects in accordance with the eligibility criteria detailed in Section 3. Before any study procedures are performed, subjects must sign an informed consent form that complies with the requirements of 45 CFR 46 and the local IRB.

Informed consent is a process that is initiated prior to an individual agreeing to participate in a trial and continuing throughout the individual's trial participation. Before any study procedures are performed, subjects' parent(s)/legal guardian(s) will receive a comprehensive explanation of the proposed study procedures and study interventions/products, including the nature and risks of the trial, alternate therapies, any known AEs, and the other elements that are part of obtaining proper informed consent. Subjects' parent(s)/legal guardian(s) will also receive a detailed explanation of the proposed use and disclosure of their protected health information. Subjects' parent(s)/legal guardian(s) will be allowed sufficient time to consider participation in the study, after having the nature and risks of the study explained to them, and have the opportunity to discuss the trial with their family, friends or legally authorized representative or think about it prior to agreeing to participate.

Informed consent forms describing in detail the study interventions/products, study procedures, risks and possible benefits are given to subjects. Informed consent forms will be IRB-approved and subjects will be asked to read and review the appropriate document. Upon reviewing the appropriate document, the site principal investigator (or designee) will explain the research study to subjects and their parent(s)/legal guardian(s) and answer any questions that may arise. The subject's parent(s)/legal guardian(s) must sign the informed consent form, and written documentation of the informed consent process is required prior to starting any study procedures/interventions being done specifically for the trial, including administering study product. Subjects will be given a copy of all informed consent forms that they sign.

By signing the informed consent form, parents/guardians give permission on behalf of their children and agree to complete all evaluations required by the trial, unless the subject withdraws voluntarily, or is withdrawn or terminated from the trial for any reason.

The rights and welfare of subjects will be protected by emphasizing to subjects that the quality of their medical care will not be adversely affected if they decline to participate in or withdraw from this trial.

Informed Consent/Assent Process

Assent will be obtained from all children following local IRB policies and standard practices for obtaining and documenting assent.

APPENDIX

[figure not shown]
Figure A1. Asthma Control Chart for Children 5-11 years of age¹⁷

Asthma Control Chart

FIGURE 3-5b. ASSESSING ASTHMA CONTROL IN CHILDREN 5–11 YEARS OF AGE

Components of Control		Classification of Asthma Control (Children 5–11 years of age)		
		Well Controlled ≤2 days/week but not more than once on each day	Not Well Controlled >2 days/week or multiple times on ≤2 days/week	Very Poorly Controlled Throughout the day
Impairment	Symptoms			
	Nighttime awakenings	≤1x/month	≥2x/month	≥2x/week
	Interference with normal activity	None	Some limitation	Extremely limited
	Short-acting beta ₂ -agonist use for symptom control (not prevention of EIB)	≤2 days/week	>2 days/week	Several times per day
	Lung function • FEV ₁ or peak flow • FEV ₁ /FVC	>80% predicted/ personal best >80%	60–80% predicted/ personal best 75–80%	<60% predicted/ personal best <75%
Risk	Exacerbations requiring oral systemic corticosteroids	0–1/year	≥2/year (see note)	
	Consider severity and interval since last exacerbation			
	Reduction in lung growth	Evaluation requires long-term followup.		
	Treatment-related adverse effects	Medication side effects can vary in intensity from none to very troublesome and worrisome. The level of intensity does not correlate to specific levels of control but should be considered in the overall assessment of risk.		

Key: EIB, exercise-induced bronchospasm; FEV₁, forced expiratory volume in 1 second; FVC, forced vital capacity; ICU, intensive care unit

Figure A2. Daily Medication Steps for Persistent Asthma¹⁷

Key: Alphabetical order is used when more than one treatment option is listed within either preferred or alternative therapy. ICS, inhaled corticosteroid; LABA, inhaled long-acting beta₂-agonist, LTRA, leukotriene receptor antagonist; SABA, inhaled short-acting beta₂-agonist

Notes:

- The stepwise approach is meant to assist, not replace, the clinical decisionmaking required to meet individual patient needs.
- If alternative treatment is used and response is inadequate, discontinue it and use the preferred treatment before stepping up.
- Theophylline is a less desirable alternative due to the need to monitor serum concentration levels.
- Step 1 and step 2 medications are based on Evidence A. Step 3 ICS + adjunctive therapy and ICS are based on Evidence B for efficacy of each treatment and extrapolation from comparator trials in older children and adults—comparator trials are not available for this age group; steps 4–6 are based on expert opinion and extrapolation from studies in older children and adults.
- Immunotherapy for steps 2–4 is based on Evidence B for house-dust mites, animal danders, and pollens; evidence is weak or lacking for molds and cockroaches. Evidence is strongest for immunotherapy with single allergens. The role of allergy in asthma is greater in children than in adults. Clinicians who administer immunotherapy should be prepared and equipped to identify and treat anaphylaxis that may occur.

Figure A3. Estimated Comparative Daily Dosages for Inhaled Corticosteroids²³

4.9 Estimated Comparative Daily Dosages for Inhaled Corticosteroids

FIGURE 18. ESTIMATED COMPARATIVE DAILY DOSAGES FOR INHALED CORTICOSTEROIDS

Drug	Low Daily Dose			Medium Daily Dose			High Daily Dose		
	Child 0–4 Years of Age	Child 5–11 Years of Age	≥12 Years of Age and Adults	Child 0–4 Years of Age	Child 5–11 Years of Age	≥12 Years of Age and Adults	Child 0–4 Years of Age	Child 5–11 Years of Age	≥12 Years of Age and Adults
Beclomethasone HFA 40 or 80 mcg/puff	NA	80–160 mcg	80–240 mcg	NA	>160–320 mcg	>240–480 mcg	NA	>320 mcg	>480 mcg
Budesonide DPI 90, 180, or 200 mcg/inhalation	NA	180–400 mcg	180–600 mcg	NA	>400–800 mcg	>600–1,200 mcg	NA	>800 mcg	>1,200 mcg
Budesonide Inhaled Inhalation suspension for nebulization	0.25–0.5 mg	0.5 mg	NA	>0.5–1.0 mg	1.0 mg	NA	>1.0 mg	2.0 mg	NA
Flunisolide 250 mcg/puff	NA	500–750 mcg	500–1,000 mcg	NA	1,000–1,250 mcg	>1,000–2,000 mcg	NA	>1,250 mcg	>2,000 mcg
Flunisolide HFA 80 mcg/puff	NA	160 mcg	320 mcg	NA	320 mcg	>320–640 mcg	NA	≥640 mcg	>640 mcg
Fluticasone HFA/MDI: 44, 110, or 220 mcg/puff	176 mcg	88–176 mcg	88–264 mcg	>176–352 mcg	>176–352 mcg	>264–440 mcg	>352 mcg	>352 mcg	>440 mcg
DPI: 50, 100, or 250 mcg/inhalation	NA	100–200 mcg	100–300 mcg	NA	>200–400 mcg	>300–500 mcg	NA	>400 mcg	>500 mcg
Mometasone DPI 200 mcg/inhalation	NA	NA	200 mcg	NA	NA	400 mcg	NA	NA	>400 mcg
Triamcinolone acetanide 75 mcg/puff	NA	300–600 mcg	300–750 mcg	NA	>600–900 mcg	>750–1,500 mcg	NA	>900 mcg	>1,500 mcg

Key: DPI, dry power inhaler; HFA, hydrofluoroalkane; MDI, metered-dose inhaler; NA, not available (either not approved, no data available, or safety and efficacy not established for this age group)

Therapeutic Issues:

- The most important determinant of appropriate dosing is the clinician's judgment of the patient's response to therapy. The clinician must monitor the patient's response on several clinical parameters and adjust the dose accordingly. Once control of asthma is achieved, the dose should be carefully titrated to the minimum dose required to maintain control.
- Preparations are not interchangeable on a mcg or per puff basis. This figure presents estimated comparable daily doses. See EPR—3 Full Report 2007 for full discussion.
- Some doses may be outside package labeling, especially in the high-dose range. Budesonide nebulizer suspension is the only inhaled corticosteroid (ICS) with FDA-approved labeling for children <4 years of age.
- For children <4 years of age: The safety and efficacy of ICSs in children <1 year has not been established. Children <4 years of age generally require delivery of ICS (budesonide and fluticasone HFA) through a face mask that should fit snugly over nose and mouth and avoid nebulizing in the eyes. Wash face after each treatment to prevent local corticosteroid side effects. For budesonide, the dose may be administered 1–3 times daily. Budesonide suspension is compatible with albuterol, ipratropium, and levalbuterol nebulizer solutions in the same nebulizer. Use only jet nebulizers, as ultrasonic nebulizers are ineffective for suspensions. For fluticasone HFA, the dose should be divided 2 times daily; the low dose for children <4 years of age is higher than for children 5–11 years of age due to lower dose delivered with face mask and data on efficacy in young children.

Potential Adverse Effects of Inhaled Corticosteroids:

- Cough, dysphonia, oral thrush (candidiasis).
- Spacer or valved holding chamber with non-breath-actuated MDIs and mouthwashing and spitting after inhalation decrease local side effects.
- A number of the ICSs, including fluticasone, budesonide, and mometasone, are metabolized in the gastrointestinal tract and liver by CYP 3A4 isoenzymes. Potent inhibitors of CYP 3A4, such as ritonavir and ketoconazole, have the potential for increasing systemic concentrations of these ICSs by increasing oral availability and decreasing systemic clearance. Some cases of clinically significant Cushing syndrome and secondary adrenal insufficiency have been reported.
- In high doses, systemic effects may occur, although studies are not conclusive, and clinical significance of these effects has not been established (e.g., adrenal suppression, osteoporosis, skin thinning, and easy bruising). In low-to-medium doses, suppression of growth velocity has been observed in children, but this effect may be transient, and the clinical significance has not been established.

Table A1. Feasibility Benchmarks

Item	Goal
Enrollment	70% of those who are approached and eligible provide consent and are enrolled in the study
Reason for non-enrollment	90% of those approached and eligible who decline to enroll will be asked for reason for refusal
Education provided at first visit is understandable	Before leaving the clinic, all parents or guardians will demonstrate: 
 • proper use and care of the digital peak flow meter • proper use and care of oral digital thermometer • proper use of study ruler to assess erythema and induration • proper use of paper and/or electronic data entry forms
Memory Aid Data Completion through Day 15	At least 80% of the patients will complete the memory aid for 11 of the 15 day monitoring period
Memory Aid Data Completion Day 16 through day 43	At least 70% of the patients will complete the memory aids for Day 16 through 43
Peak Flow measurements (early study)	At least 75% of subjects will perform and document all home digital peak flow measurements (per protocol) for on at least 11 of the 15 day monitoring period.
Peak flow measurement (late study)	At least 70% of subjects will perform and document the digital peak flow for Day 42.
Nighttime awakenings (done in am)	At least 70% of subjects will document nighttime awakenings for at for on at least 11 of the 15-day monitoring period.
Day 4 (-1 to +2) call	At least 80% of study subjects will respond to Day 4 call and provide requested data (ACT and Prose are administered on the call)
Day 8 (± 2) call	At least 80% of study subjects will respond to Day 8 call and provide requested data. (ACT and Prose are administered on the call)
Day 15 (-1 to +2) call	At least 80% of study subjects will respond to Day 15 call and provide requested data. (ACT and Prose are administered on the call)
Day 29 (± 2) call	At least 70% of study subjects will respond to Day 29 call and provide requested data.
Day 44 (+3) call	At least 70% of study subjects will respond to Day 44 call and provide requested data. (ACT and Prose are administered on the call)
Parental Satisfaction survey	At least 70% of parents will complete the Parent/Guardian satisfaction survey

Schedule of Events

Table A2.

Study Visit	Enrollment Visit 1 (Vaccination)	Visit 2	Visit 3	Visit 4	Visit 5	Visit 6
Study Day	1	4	8	15	29	43
Visit Window (Days)	n/a	3-6	7-9	14-17	27-31	44-47
Type of Visit	Clinic	Call/email	Call/email/clinic ^a	Call/email	Call/email	Call/email
Obtain Informed Consent	X					
Obtain Assent (if applicable per site's IRB requirement)	X					
Review Eligibility Criteria	X					
Document Prior Year Flu Vaccination	X					
Review Medical History	X					
Review Asthma History	X					
Assess asthma clinical symptoms ^b (PROSE)	X	X	X	X		X
Assess asthma control ^c (cACT)	X	X	X	X		X
Asthma severity classification ^d	X					
Concomitant Medications ^e	X	X	X	X	X	X
Oral temperature	X					
Height, Weight, BMI	X					
Peak Flow Measurement ^f	X	X	X	X		X
Document zip code	X					
Enrollment/Randomization ^g	X					
Study Vaccination	X					
Post vaccination evaluation period (20 minutes)	X					
Distribute Memory Aid/ Materials	X					
AE collection/Memory Aid Review	X	X	X	X		
SAE/Medical Services Utilization ^h	X	X	X	X	X	X
Parent/guardian satisfaction survey						X

^b Asthma clinical symptoms assessed using the PROSE questionnaire.

^c Asthma control assessed using the "Childhood Asthma Control Test (cACT)."

^d See section 3.3 in the protocol, for categories of asthma severity.

^e All current medications taken within 28 days prior to signing the informed consent form and through Day 43 (Visit 6).

^f The highest of 3 peak flow measurements will be recorded.

^g Subjects will be randomized 1:1 to cclIV4 or IIV4; stratified by two groups of disease severity: 1) mild persistent or 2) moderate or severe persistent.

^h Medical services utilization to include visits to doctor, urgent care, emergency room, hospitalization.

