3 ELIGIBILITY CRITERIA

3.1 Inclusion Criteria

1. Children between 5-11 years of age, inclusive, at enrollment

2. Participant must have a current diagnosis of persistent asthma¹

¹ *Physician diagnosis of asthma and current prescribed use of a daily controller medication*

3. Parent/legal guardian must provide written informed consent and subject must provide assent as appropriate for age prior to initiation of study procedures and according to local IRB requirement

4. Parent/legal guardian and subject must be willing and able to comply with planned study procedures and be available for all study visits

5. Children aged 5-8 years must have received at least 2 doses of seasonal trivalent or quadrivalent influenza vaccine prior to the current influenza season. Children 9-11 years must have received at least 1 dose of seasonal trivalent or quadrivalent influenza vaccine prior to the current influenza season.²

² *Influenza vaccination history verification Figure 2 appendix*

6. Is in good health, other than their asthma, as determined by medical history and targeted physical examination based on medical history

7. English or Spanish literate³

³ *only English speaking participants will be included at the Cincinnati site*

8. Intention of being available for entire study period and complete all relevant study procedures, including follow-up phone calls and collection of information

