4.1 Recruitment

Subject enrollment for this feasibility study will begin during September or October 2016. Site-specific information is described below.

Vanderbilt

Vanderbilt will enroll approximately 20 participants. The Vanderbilt Pediatric Pulmonary Clinic will be the source for the majority of patients enrolled. There are additional Allergy and General Pediatric Clinics that have patients with asthma but if enrolled, these patients will be referred to the Pulmonary Clinic or to the Clinical Research Center at the Children's Hospital where enrollment will occur.

The Pediatric Pulmonary Clinic has the necessary space and infrastructure to provide support for this study. Ongoing clinical research is conducted there and the investigators can integrate research enrollment in the same area as they are providing clinical care. During the months prior to enrollment, the research staff will inquire about the study interest, will assess the ability of the families to assess clinical symptoms and to perform home respiratory testing, and will identify parental preferences for recording reaction data. Drs. [name] and [name] will facilitate introduction of the patients to the study staff, and the patients will be informed about the study. During August and September 2016, when recruitment and enrollment is expected to begin, Vanderbilt Vaccine Research Program (VVRP) study staff will be actively involved in recruitment. All qualifying patients for the study will be given information and contact numbers to discuss the study in the months prior to the study onset. The research team will provide follow up contact information to discuss questions or concerns.

After informed consent, Vanderbilt study staff will target subjects with moderate or severe persistent asthma for the conduct of the study, which represents the majority of patients at this Vanderbilt clinic. Using the Severity and Control tables shown in the Appendix, subjects will be graded for each of these two parameters, severity and control, and these assessments will be recorded on the Case Report Form. Lists of children with an interest in the study will have been previously compiled prior to the availability of the vaccine. If the parents agree to participation, then the subjects will be seen in the outpatient clinic areas (e.g., Pediatric Pulmonary Clinic or Pediatric Clinical Research Center) at Vanderbilt Children's Hospital.

Cincinnati

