Cincinnati will enroll approximately 20 participants. The study population will be children with asthma who are patients at Cincinnati Children's Hospital Medical Center (CCHMC) with primary recruitment from the Pulmonary Asthma and Pediatric Primary Care (PPC) Clinics at CCHMC. One of the ongoing quality management goals at CCHMC is to document the level of severity for all children cared for at CCHMC with

asthma. Of those not categorized, Cincinnati will be able to categorize their asthma severity and control if they interested in the study.

If influenza vaccine (ccIIIV4 and IIV4) is available, Cincinnati would like to start enrollment in September 2016 to maximize the number of weeks for enrollment. Using local and national data, we will determine the target weeks for enrollment to ensure this high-risk group of children with asthma are vaccinated for influenza well before the influenza season starts. The target enrollment period should be as soon as both vaccines are available and should end by the last week of November allowing for approximately 12-13 weeks for enrollment.

Cincinnati will recruit approximately 20 children, 5-11 years of age, diagnosed with asthma of varying degrees of severity. The primary strategy for recruitment will be through the Pulmonary Asthma Clinic and the Pediatric Primary Care Center. Cincinnati will advertise at these two sites, as well as through the asthma registry and their database of past research participants who have agreed to be e-mailed for future studies. Any written communication provided to the potential subjects' parents/legal guardians about the study will be submitted to the IRB for their approval before study initiation. Recruitment letters introducing the study will be sent to parents of asthmatic children shortly ahead of the influenza vaccination season. To assist with recruitment, parents will then be called 2 to 3 weeks after sending the letter to screen for interest, eligibility and enrollment (September-November 2016). Recruitment will also be coordinated with well child visits and clinic visits. Recruitment will be advertised by the use of flyers posted in pediatric/allergy/and pulmonary clinics.

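### Does Table A1 need to define *approached* and *eligible* before the enrollment rate can be read against its 70% goal?

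*Combined protocol and SAP*

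**What the plan says.** Appendix Table A1 sets the enrollment goal as "70% of those who are approached and eligible provide consent and are enrolled in the study". Its second row uses the same base: "90% of those approached and eligible who decline to enroll will be asked for reason for refusal". Section 8 says only that the proportion meeting these benchmarks will be determined. It attaches no decision rule.

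Two criteria in Section 3.1 concern attitude and availability rather than clinical status. Criterion 4 reads "Parent/legal guardian and subject must be willing and able to comply with planned study procedures and be available for all study visits". Criterion 8 begins "Intention of being available for entire study period and complete all relevant study procedures". Written consent is itself criterion 3.

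Section 4.1 describes a different recruitment route at each site:

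- **Vanderbilt (about 20 of 50):** "During the months prior to enrollment, the research staff will inquire about the study interest, will assess the ability of the families" to assess symptoms and do home respiratory testing. Also, "All qualifying patients for the study will be given information and contact numbers to discuss the study in the months prior to the study onset", and "Lists of children with an interest in the study will have been previously compiled prior to the availability of the vaccine".
- **Cincinnati (about 20):** letters go out, then "parents will then be called 2 to 3 weeks after sending the letter to screen for interest, eligibility and enrollment". Families who look eligible and are interested get an appointment.
- **Duke (about 10):** letters may be sent, followed by a call to schedule screening and enrollment.

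Section 4.3.1 lists the full eligibility review at Visit 1, after consent. Section 10.1 mentions enrollment logs and periodic enrollment audits, but not where the count of contacts starts.

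**The concern.** Feasibility is the primary objective, and this is the first benchmark listed for it. A rate whose denominator is undefined can be computed in more than one way from the same recruitment.

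Two readings seem open. First, a family that refuses because daily peak flows, diaries and calls are too much could be logged as a decliner, which keeps it in the denominator, or as failing criterion 4 or 8, which removes it. Second, at Vanderbilt a family that says no to the pre-season inquiry could be counted as approached, or could simply never reach the interest list from which enrollment is made. Under the second choice in each case the pooled rate describes families already filtered for interest, and it would flatter the prospects of the later LAIV4 study.

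**Working it through.** **No figure to reproduce.** The 70% is a chosen goal. Section 8 states that sample sizes were predetermined and no power calculation was made. The site targets add up: 20 + 20 + 10 = 50.

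**Sensitivity to the denominator.** Rate = enrolled / (enrolled + counted eligible families who do not enroll), with 50 enrolled.

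- Largest denominator that meets the goal: 50/0.70 = 71.4, so 71.
- 50/71 = 70.4% (met); 50/72 = 69.4% (missed). At most 71 − 50 = 21 eligible non-enrollers can be counted.
- Near the goal, one family moves the rate by about 1 percentage point.
- Assumed illustration, five families either way from 71: 50/66 = 75.8% and 50/76 = 65.8%.
- Exact 95% interval at 50/71: 58.4% to 80.7%, wider than that illustration.

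**Criteria 4 and 8.** Assume 30 decliners.

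- All counted as eligible decliners: 50/80 = 62.5%.
- Half reclassified as ineligible: 50/65 = 76.9%.
- All reclassified: 50/50 = 100%.

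The last case shows why this reading is not the intended one. It would leave the second row with nobody to ask for a reason. That row presupposes people who are eligible and still decline. A decliner necessarily fails criterion 3, so consent cannot be part of *eligible* here, and the same reasoning covers unwillingness under criteria 4 and 8. Section 4.1 agrees: for Cincinnati it names interest and eligibility as separate things, both in the screening call and in the condition for an appointment. Only genuine inability or unavailability remains arguable.

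**Which contact is the approach.** Counting families who were mailed a letter and never replied would lower the rate. With 10 assumed decliners, 50/60 = 83.3%; adding 20 silent families gives 50/80 = 62.5%. But a family that has not answered is not known to be eligible and has not declined, so it fits neither row. Cincinnati and Duke both follow letters with calls, and the call is the natural point to start the count.

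At Vanderbilt, Section 3.2 helps. Exclusions cover illness or fever within 72 hours, antipyretics within 24 hours, systemic steroids for an exacerbation within 28 days, recent vaccines, and receipt of the current year's influenza vaccine. None of these can be judged months ahead. Being both approached and eligible is therefore most naturally assessed in the enrollment season. Leaving early refusals out on that reading raises the pooled rate. Vanderbilt supplies 20/50 = 40% of planned enrollment, but no contact counts are given, so the rise cannot be sized.

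**Direction.** Reclassifying burden refusals and omitting early refusals both shrink the denominator and raise the rate. A pull downward comes from the order of events at Visit 1: consenters who then fail a clinical criterion drop out, while decliners who would have failed are never examined and stay in. That follows from seeking consent before full review, and defining the two words would not remove it.

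**The case for a change.** The strongest argument for a change is timing. Pre-season contacts that nobody logs may be impossible to reconstruct, so a definition is worth most before recruitment opens. It would cost a short table note and a few log codes, and it concerns the primary outcome. Three recruitment routes pooled into one percentage do deserve a stated starting point.

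Part of this stands. The plan does not name the contact that starts the count at each site, and a report that gave the rate without saying so would be harder to interpret.

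The argument loses force in three places. Counting Vanderbilt families from the first inquiry would put refusers in the denominator whose time-bound exclusions could not yet be assessed, which enlarges the downward pull from unexamined decliners; it is a preference rather than a correction. The benchmark is an acceptance rate among eligible families, so it does not tell planners how many families to contact per child enrolled under any definition of the two words. And the primary outcome includes a qualitative account of best practices and lessons learned, where differences between site recruitment routes and Vanderbilt's early refusals can be described.

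**Conclusion.** The wording gap is real, but it calls for no change. No rule in the plan produces a wrong rate. The second row of Table A1 largely settles criteria 4 and 8, and the time-bound exclusions favor the enrollment-season contact. Site staff can settle the rest sensibly when they keep their enrollment logs, and the report can say where each site's count began.

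The possible effect is about 1 percentage point per family near the goal. The five-family span of 65.8% to 75.8% rests on an assumed number of families and on 50 being enrolled. The true size is unknown because the documents give no counts of families contacted or declining. No go/no-go decision turns on crossing 70%, and the sampling uncertainty at 50/71 is wider than that span.
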